### 6.7.2 Safety Analysis Set (SAS)

The SAS is identical to the FAS, which will include patients who were enrolled, allocated to treatment, and received at least one non-zero dose of study treatment.

This analysis population will be used for the analysis of safety and exposure.

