## 6.8 Data Display Characteristics

Data displays produced for this study will include three types—summary tables, data listings, and figures. Unless stated otherwise, data listings will be produced for all recorded data. Additional data listings will be produced for outcome measures that involve extensive procedures to derive the analyzed outcomes. Summary tables and figures will be produced when specified in sections to follow. All analyses will be performed using SAS (Statistical Analysis Software).

Data listings will simply list the data recorded on the CRF or derived for each subject. As needed, they can be ordered by dose cohort, site, subject number, and time of assessment, and additional levels of ordering hierarchy may reflect subsets of assessments within subject. Subject-level identifiers appear on the first line of data, and identifiers for subgroups within subject appear only on the first line of each subgroup value.

Tables will display summary statistics calculated for each dose cohorts per study phase (escalation/expansion), unless described otherwise in the following sections. For most summary tables, the dose group will be presented in column and the summary statistics of interest will be presented in rows. About tables labelling, the text “Number (%) of Subjects” will be incorporated in the title, either the primary title or as a separate subtitle, and no further labeling (e.g., “n (% )”) will appear in the body of the table.

The summary statistics displayed will be a function of the type of data associated with the summarized assessment. Unless stated otherwise in relevant sections to follow, continuous data will be summarized with the number of non-missing values, mean, standard deviation, minimum, median, and maximum. Categorical data will be summarized with the number of non-missing values and the numbers of values equal to each of the possible values. Percentages of subjects with each of the possible values will be calculated from the number of subjects in the corresponding analysis population, unless stated otherwise, and those percentages will be presented with one decimal (XX.X%). Some continuous variables may also be grouped into categorical levels and evaluated in frequency tables.

Pfizer Inc. / Protocol: TTI-621-03/C4961003  
IQVIA Biotech (Confidential) Project # YXA42460

Dates in the clinical database are classified into the categories of procedure dates, log dates, milestone dates, outcome dates, and special dates:

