## 9. Safety Analyses

Summary of AEs and other safety parameters will be based on the SAS by treatment group as described in Section 6.1, except for the DLT, which will be based on DLT-Evaluable Set (DES) by treatment group.

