### 9.1 Exposure

In the combination portion of the study, Cycle 1 through Cycle 6, doxorubicin will be administered at 75 mg/m^2 on Day 1 of each 21-day cycle. A maximum of six cycles of doxorubicin (18 weeks of treatment) is permitted.

In Cycle 1 through Cycle 6, PF-07901800 will be administered by intravenous infusion over 120 minutes on Day 1 and Day 8 of each 21-day cycle. Beginning with Cycle 7, PF-07901800 will be administered as monotherapy on Day 1 and Day 15 of 28-day cycles until documentation of disease progression or unacceptable toxicity. Monotherapy will be considered starting on the first cycle without doxorubicin.

PF-07901800 dose levels planned for evaluation in combination with doxorubicin in the dose escalation portion of the study are as follow:

Dose Level	PF-07901800 Dose
1	0.2 mg/kg
2	0.7 mg/kg
3	2.0 mg/kg

During the dose expansion portion of the study, two dose levels of PF-07901800 are planned to be evaluated in combination with fixed-dose

Pfizer Inc. / Protocol: TTI-621-03/C4961003  
IQVIA Biotech (Confidential) Project # YXA42460

doxorubicin. The low dose of PF-07901800 is anticipated to be 0.2 mg/kg and the high dose is anticipated to be the maximum of other PF-07901800 dose levels evaluated in the dose escalation portion of the study, prospectively planned to be 2.0 mg/kg, but alternate dose levels may require evaluation and a different dose may be taken forward based after discussion with treating physicians and the Sponsor.

Exposure to PF-07901800 and doxorubicin will be summarized with descriptive statistics for the number of non-zero doses received, duration of dosing (weeks), total cumulative dose (mg/kg for PF-07901800, mg/m^2 for doxorubicin).

Total cumulative dose is the sum of the actual doses of PF-07901800 or doxorubicin received.

Duration of dosing is defined as the time (in weeks) from first dose of study drug in cycle 1 to the last dose of study drug in the last cycle a patient had.

The calculation algorithm for duration of exposure (in days) for each drug will be:

- Doxorubicin:
  - o Last Doxorubicin dose date – first Doxorubicin dose date + 21
- PF-07901800:
  - o If the last dose is on Day 1 of Cycles 1-6: (Last PF-07901800 dose date – first PF-07901800 dose date + 7)
  - o If the last dose is on Day 8 of Cycles 1-6, and any time after Cycle 6: (Last PF-07901800 dose date – first PF-07901800 dose date + 14)

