### 9.3 Adverse Events

Adverse events (AEs) will be documented on the AE eCRF and monitored continuously throughout the study. Adverse events will be coded using the Medical Dictionary for Regulatory Activities (MedDRA), latest version, associating lower-level terms with PT and SOC by the primary hierarchy.

Treatment Emergent Adverse Events (TEAEs) are those events with onset date occurring during the on-treatment period. The tables will display counts and percentages of patients who reported at least one TEAE in each SOC represented in the AE data. Within each SOC, the tables will display the counts and percentages of patients reporting at least one TEAE, as designated by the PT.

The severity of adverse events will be graded using the NCI Common Toxicity Criteria for Adverse Events (CTCAE version 5.0). The intensity is assigned a grade of 1 through 5 using the following CTCAE guidelines: Grade 1 – Mild; Grade 2 – Moderate; Grade 3 – Severe; Grade 4 – Life-threatening; Grade 5 – Death.

The causality of AE are reported as either related to study drug or not related to study drug for each study drug. Related AEs are those related to any study drug (i.e., at least one of the study drugs).

Pfizer Inc. / Protocol: TTI-621-03/C4961003  
IQVIA Biotech (Confidential) Project # YXA42460

If a patient has multiple occurrences of an adverse event, the strongest level of relationship to study drug(s) and the worst toxicity grade a patient experiences for a given AE will be used in these tables. No imputation will be performed for missing toxicity grade or causality data.

AEs that have missing onset dates will be considered as TEAE unless the stop date is known to be prior to the first administration of the study medication. If the AE onset date is partial, the date will be correlated as far as possible with the date of first dose of study medication. AE will be assumed to be TEAE, unless there is clear evidence (through comparison of partial dates) to suggest that the adverse event started prior to the first dose of study medication. Detailed imputation rules can be found in section 6.3. If patients died during the study and experienced AEs at the time of death, the AEs that lead to death will use death date as the AE end date; otherwise, AEs that do not lead to death will be reported as ongoing.

Adverse Events of Special Interest (AESI) include the following:

- Thrombocytopenia: Haematopoietic thrombocytopenia – SMQ Broad

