- Anemia: Haematopoietic erythropenia – SMQ broad
- Hemorrhage: Haemorrhage terms (excl. laboratory terms) – SMQ narrow
- Infusion related reactions (PT of Infusion-related reaction as recorded on the Adverse Event CRF)

The following TEAE summary tables will be produced by treatment group as described in Section 6.1:

- a. An overall summary of safety will summarize the numbers (and percentages) of patients with the following:
  - TEAEs (separately for combination period and monotherapy period, and overall), where combination period is defined as from the date of first study treatment to the date of last doxorubicin + 21 days
  - Grade  $\geq 3$  TEAEs (separately for combination period and monotherapy period, and overall)
  - Treatment-related TEAEs (separately for combination period and monotherapy period, and overall)
  - Treatment-related grade  $\geq 3$  TEAEs (separately for combination period and monotherapy period, and overall)
  - Serious TEAEs
  - Treatment-related Serious TEAEs
  - TEAEs leading to dose reduction (of PF-07901800 and doxorubicin, separately)
  - TEAEs leading to drug interruption (of PF-07901800 and doxorubicin, separately)

Pfizer Inc. / Protocol: TTI-621-03/C4961003  
IQVIA Biotech (Confidential) Project # YXA42460

- TEAEs leading to permanently discontinued study drug (PF-07901800, doxorubicin, and both)
- Treatment related TEAEs leading to permanent discontinuation of PF-07901800
- Treatment-related TEAEs leading to permanent discontinuation of doxorubicin
- Treatment-related TEAEs leading to permanent discontinuation of both drugs
- TEAEs leading to death
- Treatment-related TEAEs leading to death
- At least one TEAE of special interest: Thrombocytopenia SMQ (broad)
- At least one TEAE of special interest: Anemia SMQ (broad)
- At least one TEAE of special interest: Hemorrhage SMQ (narrow)
- At least one TEAE of special interest: Infusion related reactions

b. Separate summaries of TEAEs by SOC and PT, as follows:

- TEAEs by maximum severity (separately for combination period and monotherapy period, and overall)
- Treatment-related TEAEs (separately for combination period and monotherapy period, and overall)
- DLT
- Serious TEAEs
- Treatment-related Serious TEAEs
- TEAEs leading to dose reduction (of PF-07901800 and doxorubicin separately)
- TEAEs leading to drug interruptions (of PF-07901800 and doxorubicin separately)
- TEAEs leading to permanent discontinuation (of PF-07901800 and doxorubicin separately, and both)

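### Adverse event percentages for the monotherapy period use all treated patients as denominator, so under the SAP's own definition of monotherapy they understate the rate among patients who received it

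*SAP*

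**What the plan says.** SAP 9.3 states that "The tables will display counts and percentages of patients who reported at least one TEAE". Its overall safety summary then asks for "TEAEs (separately for combination period and monotherapy period, and overall), where combination period is defined as from the date of first study treatment". The end of that period is set as "to the date of last doxorubicin + 21 days". The same split applies to Grade 3 or higher, treatment-related, and treatment-related Grade 3 or higher events. It is repeated in the tables by system organ class and preferred term for maximum severity and for treatment-related events.

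Three other statements fix the denominator:

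- SAP 9: "Summary of AEs and other safety parameters will be based on the SAS by treatment group as described in Section 6.1". The only exception is dose-limiting toxicity.
- SAP 6.7.2: "The SAS is identical to the FAS, which will include patients who were enrolled, allocated to treatment, and received at least one non-zero dose".
- SAP 6.8: percentages "will be calculated from the number of subjects in the corresponding analysis population, unless stated otherwise".

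SAP 6.7 defines only the FAS, the SAS and the DLT-evaluable set. There is no set of patients who entered monotherapy.

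On timing, SAP 9.1 says "Monotherapy will be considered starting on the first cycle without doxorubicin", which is normally Cycle 7. Protocol 5.2.2 allows a switch at Cycle 5 or 6 after at least four combination cycles. SAP 9.3 gives no start or end date for the monotherapy period.

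**The concern.** Every SAS patient enters the combination period, so the SAS is the right denominator for those columns. It is not right for the monotherapy columns, because a patient who stops both drugs during the combination cycles has no monotherapy exposure but still counts in the denominator.

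Safety in combination and then as monotherapy is a primary objective of the expansion (SAP 2.1), and the expansion safety profile is a secondary endpoint (SAP 3.2). The period columns of SAP 9.3 are the only adverse event tables split between the two. The tables for events of special interest, including thrombocytopenia, are not split by period.

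This matters clinically. Protocol Table 22 returns patients whose TTI-621 was reduced for thrombocytopenia to their starting dose level when they move to monotherapy. SAP 4.3.2 records that Cohort B was closed to further enrolment because of Grade 3 or 4 thrombocytopenia during combination. A reader asking how patients fare after that re-escalation will look at the monotherapy columns and see a diluted rate. If cohorts differ in the share who reach monotherapy, they are diluted by different amounts.

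**Working it through.** The plan states no figure here, so there is none to reproduce. The check has three parts.

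**1. Denominator.** SAP 9.3 sets the table, SAP 9 sets the population, and SAP 6.8 divides by that population unless stated otherwise. Nothing in SAP 9.3 states otherwise. Let N be the number in the SAS, s the share who start monotherapy as defined in SAP 9.1, and r the proportion of starters with an event. Then:

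printed percentage = (r × s × N) / N = r × s

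**2. Size.** The documents do not give s, so this part is an illustration. Inputs: combination treatment lasts 18 weeks (126 / 30.4375 = 4.14 months), or 12 weeks (84 / 30.4375 = 2.76 months) for the earliest switch. Both documents quote progression-free survival of 3-5 months on doxorubicin. Assumptions: that range is a median m, survival is exponential, and reaching week t progression-free stands in for starting monotherapy. Then s = 0.5^(t/m).

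| Median m | s at 18 weeks | 30% among starters prints as | s at 12 weeks |
|---|---|---|---|
| 3 months | 38.4% | 11.5% | 52.9% |
| 4 months | 48.8% | 14.6% | 62.0% |
| 5 months | 56.3% | 16.9% | 68.2% |

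At 18 weeks the understatement is a factor of 1/0.563 = 1.8 to 1/0.384 = 2.6.

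For single events, take the cohort sizes in SAP 4.3.2 (A planned at 31, B 18, C 13) and the 18-week shares:

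- A: about 12-17 starters. One event prints as 1/31 = 3.2%, against 1/17 = 5.9% to 1/12 = 8.3% among starters.
- B: about 7-10 starters. 1/18 = 5.6%, against 1/10 = 10.0% to 1/7 = 14.3%.
- C: about 5-7 starters. 1/13 = 7.7%, against 1/7 = 14.3% to 1/5 = 20.0%.

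**3. Period boundary.** On schedule, Cycle 6 Day 1 is day 5 × 21 + 1 = 106. Adding 21 gives day 127, which is also Cycle 7 Day 1 (6 × 21 + 1). SAP 9.1 and SAP 9.3 therefore agree except for one shared day.

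The trouble arises if the monotherapy period is programmed as all on-treatment time after the combination period. SAP 6.4 runs on-treatment time to 30 days after the last dose, or to new anti-cancer therapy if earlier. For a patient who stops both drugs on schedule:

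- Last TTI-621 on Day 1: 30 − 21 = 9 days are labelled monotherapy.
- Last TTI-621 on Day 8: 7 + 30 − 21 = 16 days.

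So up to 9-16 days count as monotherapy in a patient who never received it. Under this reading non-starters can contribute events, and r × s is no longer exact.

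**The case against.** **Percent of all treated patients is a legitimate description of a planned sequence.** This stands in part. The overall columns already describe the whole sequence, though. A column labelled as the monotherapy period will be read as risk during monotherapy.

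**The number of starters can be recovered.** A reader might infer that the denominator is hidden, but the documents do not support that. SAP 9.6 summarises vital signs by visit, and SAP 6.8 requires the number of non-missing values. A planned table will therefore show n at Cycle 7 Day 1 for each cohort, and the swimmer plots show treatment duration. That n is a fair approximation, but it is not a stated denominator for the adverse event table. It also misses patients who switch at Cycle 5 or 6 and stop before Cycle 7. The exposure section does not supply the count either: "Exposure to PF-07901800 and doxorubicin will be summarized with descriptive statistics for the number of non-zero doses received, duration of dosing (weeks") and cumulative dose, for each drug rather than each period.

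**Other safety data are split in time.** This is correct: vital signs and LVEF are summarised by visit. The point is limited to adverse event tables.

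**Differences between cohorts could be large.** A reader might infer that a more toxic dose would look safer because fewer patients reach monotherapy. The mechanism is possible, but the documents give no cohort-specific shares, so no gap between cohorts can be sized.

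**Table shells may settle it.** None are in the documents. The SAP restricts the population where it means to, as it does for dose-limiting toxicity.

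**The events themselves are not lost.** This stands. Counts are printed beside the percentages.

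**Conclusion.** The denominator problem follows from stated rules and not from missing detail. Under the SAP 9.1 definition, the monotherapy percentages understate the rate among patients given monotherapy by the factor s. In the illustration, a 30% rate prints as about 11.5-17%. That range rests on exponential progression-free survival, on a figure quoted for doxorubicin and not for this combination, and on progression alone deciding who starts. Dropout for toxicity would lower the share. Treatment beyond progression (Protocol 5.3) or a switch at Cycle 5 or 6 would raise it.

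Two stronger readings are not supported. First, non-starters are not event-free under every reading: SAP 9.3 dates only the combination period, so a remaining-time definition could let them add events. Second, no trial decision is at risk, because no stopping rule or dose rule uses these percentages. What is affected is how the report describes monotherapy safety, which is part of a primary objective. That is worth correcting before database lock, but it does not threaten the study.

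**What to change.** In SAP 9.3:

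- Start the monotherapy period on the date of the first TTI-621 dose in the first cycle without doxorubicin, in line with SAP 9.1.
- Assign all other on-treatment time to the combination period, including all on-treatment time of patients who never receive such a dose.
- Use SAS patients who received that dose as the denominator for the monotherapy columns. Keep the full SAS for the combination and overall columns.
- Print that N, and the median weeks in the period, in the column header.
- Add a footnote that starters are a selected group and that the columns are descriptive and do not compare doses.

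The cost is two or three sentences and one derived date flag. Actual dosing dates are already collected and listed (SAP 9.1), so no patients, visits or procedures are added. The downside is small: denominators will be low, so one event moves the percentage a good deal, and selection of starters and time at risk remain unadjusted.

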#### 4.5 Assessment Schedule

The study participation for a patient might include the Screening Visit (Day -28 to -1); Cycle 1 (21-days cycle), Day 1 and Day 8; Cycle 2 to 6 (21-days cycles), Day 1 and Day 8 ( $\pm$  1 day); Subsequent Cycles (28-days cycles), Day 1 and Day 15 ( $\pm$  3 days); 7 ( $\pm$  3 days) after last administration of study treatment; Safety Follow-up Period (30 + 5 days after last administration of study treatment or before initiation of subsequent anti-cancer therapy, whichever occurs soonest); and Long-Term Follow-Up, assessed every 12  $\pm$  2 weeks.

The protocol provides additional details in Section 11.

Pfizer Inc. / Protocol: TTI-621-03/C4961003  
IQVIA Biotech (Confidential) Project # YXA42460

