## 6.4 Definition of on-treatment period

Safety endpoints will be summarized based on the on-treatment period, unless otherwise specified.

On-treatment period is defined as the time from the first dose of study treatment through minimum (30 days + last dose of study treatment, start day of new anti-cancer therapy captured on the “Survival Status” CRF).

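### SAP 9.3 splits adverse events into combination and monotherapy periods but defines only the first, and its 21-day end date fits neither the monotherapy start in 9.1 nor the TEAE window in 6.4

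*SAP*

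**What the plan says.** - **Combination period (SAP 9.3):** "where combination period is defined as from the date of first study treatment to the date of last doxorubicin + 21 days". Section 9.3 gives no start, end or denominator for the monotherapy period. It nevertheless requires the split in four overview rows (all TEAEs, Grade 3 or higher, treatment-related, treatment-related Grade 3 or higher) and in two SOC/PT tables (maximum severity, treatment-related).
- **Monotherapy start (SAP 9.1):** "Monotherapy will be considered starting on the first cycle without doxorubicin". This is the only start rule in the SAP. It stands in the exposure section, and 9.3 does not refer to it.
- **TEAE window:** TEAEs "are those events with onset date occurring during the on-treatment period" (SAP 9.3). That period runs from the first dose "through minimum (30 days + last dose of study treatment, start day of new anti-cancer therapy" (SAP 6.4).
- **Visit schedule (SAP 4.5):** "Cycle 2 to 6 (21-days cycles), Day 1 and Day 8", with a window of one day either way, then "Subsequent Cycles (28-days cycles), Day 1 and Day 15", with a window of three days either way.
- **Denominator:** "Summary of AEs and other safety parameters will be based on the SAS by treatment group as described in Section 6.1" (SAP 9). SAP 6.8 takes percentages over the analysis population unless told otherwise, and 9.3 makes no exception for the monotherapy columns.

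**The concern.** A two-period split should place each TEAE in one period and report each percentage over a population the reader can identify. Here the end of one period, the start of the other and the end of the TEAE window come from three rules that were not written to meet.

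Safety in combination and then as monotherapy is a primary objective of the expansion (SAP 2.1), although the matching endpoint is secondary (SAP 3.2). SAP 4.3.2 also records that Cohort B enrollment was ended because of Grade 3 or 4 thrombocytopenia on Day 8 of combination therapy, so readers are likely to compare the two phases.

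The first monotherapy infusion is a sensitive place for an unclear label. Infusion reactions usually begin during or soon after infusion (Protocol Table 11, note), and most platelet falls came within 24 hours of it (Protocol 3.8.1).

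**Working it through.** Let d be the date of the last doxorubicin dose.

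**Inputs.** 21-day cycles, at most six, with TTI-621 on Days 1 and 8 (SAP 9.1). Combination period ends at d+21 (SAP 9.3). TEAE window ends 30 days after the last dose of either drug, or earlier if new therapy starts (SAP 6.4; Protocol 13.3 counts both drugs as study treatment). Visit windows from SAP 4.5.

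**Step 1: the plan's own timeline.** 6 × 21 = 126 days = 18 weeks, as SAP 9.1 states. Cycle 6 Day 1 is study day 1 + 5 × 21 = 106. The 9.1 exposure formula (last dose minus "first Doxorubicin dose date + 21") gives 106 − 1 + 21 = 126 days, ending on study day 126, which is d+20. The 9.3 period ends on 106 + 21 = study day 127, which is d+21. Planned Cycle 7 Day 1 is 1 + 6 × 21 = study day 127, the same day.

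**Step 2: both drugs stopped in Cycles 1 to 6, no monotherapy.** With an inclusive end date:

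| Last dose | TEAE window ends | TEAE days after the combination period |
|---|---|---|
| Day 1 (d) | d+30 | 30 − 21 = 9 |
| Day 8 (d+7) | d+37 | 37 − 21 = 16 |
| Day 8 given one day late, Cycles 2–6 (d+8) | d+38 | 38 − 21 = 17 |

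An exclusive end date adds one day to each row. An earlier start of new anti-cancer therapy shortens them. Under the 9.1 start rule these days are in neither period. If monotherapy is read as whatever follows the combination period, they count as monotherapy in a patient who received none.

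**Step 3: transition inside the three-day window, under the 9.1 start rule.**

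| Cycle 7 Day 1 | End date inclusive | End date exclusive |
|---|---|---|
| 3 days early (d+18) | d+18 to d+21: 4 days in both periods | d+18 to d+20: 3 days in both |
| On schedule (d+21) | 1 day in both | none |
| 3 days late (d+24) | d+22 to d+23: 2 days in neither | d+21 to d+23: 3 days in neither |

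If monotherapy is read as the remainder, nothing is counted twice. However, the first monotherapy infusion is then labelled combination whenever it is early, and also when it is on schedule if the end date is inclusive.

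**Step 4: denominator.** Let r be the event rate among patients who received monotherapy and f the share of the SAS who did. The printed percentage is f × r. The documents do not give f. Purely as an illustration, with f assumed to lie between 0.4 and 0.7 (no source) and r = 30%, the table would print 0.4 × 30% = 12% to 0.7 × 30% = 21%.

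**The case against.** The strongest reply is that 9.3 does not cite 9.1. In a two-way split with one period defined, the other can fairly be read as the remainder. The gap and double counting then disappear. That stands, so both are conditional on the 9.1 rule, and the on-schedule overlap also needs an inclusive end date, which the SAP does not settle. But the remainder reading brings its own mislabelling (Steps 2 and 3), so the 21-day end date misplaces some events either way.

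Other replies also stand:
- The 9.1 exposure formula measures duration and does not assign adverse events, so its ending a day earlier is not a contradiction.
- The tables count patients, so an event changes a period row only if the patient has no other qualifying event there. In the earlier intravenous TTI-621 study, 95% of subjects had a TEAE and 82% a related one (Protocol 3.5.2.1.2), so the any-TEAE row should seldom move. Grade 3 or higher and single-term rows could.
- Toxicity that delays Cycle 7 will usually have begun before the cut-off.
- A percentage of all treated patients is a valid incidence. Counts are printed, dosing dates are listed (SAP 9.1), and SAP 7.2 tabulates completion or discontinuation of each drug. None of these is the number entering monotherapy, since some patients may switch after four cycles (Protocol 5.2.2) and completing doxorubicin does not guarantee a further TTI-621 dose.

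A reader might also infer a much longer gap by adding the 42-day toxicity hold of Protocol 9.2.1 to a Day 8 dose: 7 + 42 = d+49, leaving d+22 to d+48, or 27 days. The documents do not support that as a size. Section 9.2.1 does not say when the 42 days start. The withdrawal criteria that do count from the last dose give 42 days in the Synopsis and 21 days in section 5.3, and those passages must be reconciled.

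**Conclusion.** The point holds as a minor one, with medium confidence. SAP 9.3 requires a monotherapy split without defining that period, and the end date it sets for the other period does not fit the rest of the SAP. For a patient who stops both drugs during Cycles 1 to 6, the affected stretch is 9 or 16 days (17 with the visit window), fewer if new therapy starts. A Cycle 7 that begins one to three days early falls inside the combination period whether or not the end date is inclusive. These are days, not events, and the documents give no event rate for them.

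Monotherapy percentages over the SAS are lower than the rate among patients exposed, by the factor f. No specific understatement can be claimed, because f is not in the documents.

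A reader might infer that late TEAEs are lost, that monotherapy rates are lowered by the gap, or that the trial's safety conclusions are in doubt. None of these follows. Gap events remain in the overall column, and the gap by itself takes nothing out of the monotherapy rows. Overall, serious, discontinuation, death, AESI, laboratory and ORR results do not use the split, and neither does any decision rule. Nor should the two period rows be expected to add up to the overall row, since one patient can have events in both.

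**What to change.** In SAP 9.3:
- Define the combination period as the first dose to the day before the first TTI-621 dose of the first doxorubicin-free cycle. If there is no such dose, it runs to the end of the on-treatment period.
- Define the monotherapy period as that TTI-621 dose to the end of the on-treatment period. Each TEAE then falls in exactly one period.
- Base monotherapy percentages on SAS patients with at least one monotherapy dose, and print that N in each split table.
- Add a footnote that events arising during a delayed transition are labelled combination.

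The cost is a few lines of SAP text, one derived date from dosing dates already collected, and one N row per split table. There are two downsides. Some late events after a delayed transition will carry the combination label, hence the footnote. Monotherapy denominators will also be smaller: at the assumed 0.4 to 0.7, about 12 to 22 of 31 (12.4 to 21.7), 7 to 13 of the 18-patient cohort (7.2 to 12.6) and 5 to 9 of the 13-patient cohort (5.2 to 9.1).
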